5.9 Compliance

Overall compliance to study drug will be calculated for each subject based on actual study drug taken (mg) and the expected study drug taken (mg) over the course of Part B.

Actual study drug taken will be calculated as the sum of study drug taken from each bottle where study drug taken from each bottle is the number of capsules taken multiplied by capsule strength.

Expected study drug taken will be calculated based on the protocol-defined treatment regimen. Subjects experiencing eligible flare-ups are expected to take 20 mg for 28 days followed by 10 mg for 56 days (or longer if treatment is extended). If the number of days of treatment is extended, weight-adjusted doses, and dose reductions should be taken into account in this calculation. Subjects in the Adult Cohort who are taking non-flare-up treatment are expected to take 5 mg each day they are not taking flare-up based treatment.

For example, if a subject in the Adult Cohort took 90 5-mg capsules from bottle 1, 28 20-mg capsules from bottle 2, and 50 10-mg capsules from bottle 3, then the actual study drug taken is equal to $90 \times 5 + 28 \times 20 + 50 \times 10 = 1510$ mg. The subject started non-flare-up based treatment on Study Day 1, started flare-up based treatment on Study Day 11, and completed Part B on Study Day 174. Treatment was not extended for this flare-up, and doses were not weight-adjusted or reduced. Therefore, the subject was expected to take 20 mg for 28 days followed by 10 mg for 56 days for the flare-up and 5 mg for 90 days (174 total days in Part B – 84 days of flare-up based treatment). Expected study drug taken = $90 \times 5 + 28 \times 20 + 56 \times 10 = 1570$ mg. Compliance would be calculated as: $1510 \text{ mg} / 1570 \text{ mg} = 96.2\%$.

Percent compliance will be summarized for the Treated Population with descriptive statistics. Categories of percent compliance ($<80\%$, $\geq 80\%$) will be summarized for the Treated Population with counts and percentages of subjects.

6 Efficacy Data

Efficacy data for flare-up based treatment assessments will generally be presented by the following treatment groups for the Flare-up Population: PVO 20/10 mg, Prior Non-Flare-up/PVO 20/10 mg, and Combined PVO 20/10 mg. The primary efficacy analysis and other selected efficacy analyses will also be performed using the Flare-up PP Population.

Imaging Reads

Imaging data includes results from CT scan, x-ray, MRI, US, and WBCT scan. Results will be read and interpreted using the Primary Read process only.

The Primary Read review will be performed by two independent musculoskeletal radiologists during the study as images are made available. If there is sufficient agreement between the independent reviews, both will be used for analysis. If there is insufficient agreement between the independent reviews, an adjudication review will be performed and used for analysis. The definition of what constitutes agreement between the independent reviews is described in the PVO-1A202 FOP Independent Review Charter, version 10, dated 16Feb2017. Imaging procedures performed (categorized as “Yes”, “Yes but not evaluable”, or “No”) will be summarized at scheduled visits with counts and percentages of subjects or flare-ups as appropriate.

6.1 Primary Efficacy Endpoint

The primary efficacy endpoint is the proportion of flare-ups with no new HO at Week 12 as assessed by CT scan (or by x-ray for subjects unable to undergo CT scan). Note that “no new HO at Week 12” means no new HO at Week 12 compared to baseline where baseline is Flare-up Day 1 and Week 12 is Week 12 for subjects who completed treatment at Week 12.

Similar analyses will be performed for subjects who had extended treatment. This data will be referenced as the EOT time point.

The primary efficacy endpoint will be presented for the Flare-up Population and the Flare-up PP Population for the following treatment groups: PVO 20/10 mg, Prior Non-Flare-up/PVO 20/10 mg, and Combined PVO 20/10 mg.

The presence of “HO at baseline” and the incidence of “No new HO”, “New HO at Week 12”, and “New HO at EOT” will be summarized with counts and percentages of flare-ups. The asymptotic 95% confidence intervals for the proportions will be presented.

Similar analyses will be performed for subgroups defined by baseline edema (missing, no edema, and any edema) and baseline edema severity (no edema, any edema, mild edema, moderate edema, severe edema, and moderate or severe edema [higher-intensity flare-ups]). See Section 6.2.5 for a description of edema determination.

6.2 Secondary Efficacy Endpoints for Flare-up Based Treatment

The secondary efficacy endpoints for Flare-up based treatment will be presented by treatment group (PVO 20/10 mg, Prior Non-Flare-up/PVO 20/10 mg, and Combined PVO 20/10 mg) for the Flare-up Population and the Flare-up PP Population.

Secondary efficacy endpoints for flare-up based treatment include:

1. Change from baseline in amount of bone formation (volume) as assessed by low-dose CT scan at Flare-up Week 12 and EOT.
2. Presence of soft tissue swelling and/or cartilage by MRI at Flare-up Week 12 and EOT; or presence of soft tissue swelling by US at Flare-up Week 12 and EOT in subjects unable to undergo MRI.
3. Change from baseline in active ROM measured by goniometer at the flare-up site at Flare-up Week 12 and EOT.

4. Change from baseline in ROM as assessed by CAJIS at Flare-up Week 12 and EOT.
5. Subject and Investigator global assessment of movement at the flare-up site at Flare-Up Week 12 and EOT.
6. Change from baseline in physical function using age-appropriate forms of the FOP-PFQ at Flare-up Weeks 4, 8, 12, and EOT.
7. Change from baseline in physical and mental health using age-appropriate forms of the PROMIS Global Health Scale at Flare-up Weeks 4, 8, 12, and EOT.
8. Change from baseline in the use of assistive devices and adaptations for daily living by FOP subjects at Flare-up Week 12 and EOT.
9. Change from baseline in cartilage, bone, angiogenesis, and inflammation biomarkers at Flare-up Weeks 4, 8, 12, and EOT.
10. Duration of active, symptomatic flare-up (start date and end date), as assessed by the subject and the Investigator.
11. WBCT Volume at Baseline, Month 12, and Change from Baseline to Month 12. Similar analyses will be performed for subjects with a new HO at Month 12 and for subjects with no new HO at Month 12.

Baseline for flare-up based assessments is Flare-up Day 1.

6.2.1 Volume of HO and HO Grades

The volume of HO and HO grades (defined below) will be determined from CT imaging.

The volume of HO at baseline will be calculated as the sum of the volumes for each lesion. The volume of *new* HO at post-baseline visits will be calculated as follows:

1. If there is no new HO, assign new volume = 0. (NVOL = 0)
2. If there is new HO
 - a. Subtract the volume of baseline HO from the volume of post-baseline HO for each lesion (new volume at each lesion = $NVOL_1, NVOL_2, \dots, NVOL_L$ where L is the number of lesions).
 - b. If the volume of post-baseline HO < the volume of baseline HO for a given lesion i , impute new volume = 0 ($NVOL_i = 0$).
 - c. Calculate the total volume of new HO ($NVOL = NVOL_1 + NVOL_2 + \dots + NVOL_L$).

If an adjudication review is performed, the volume from the adjudication review will be used for analysis. Otherwise, the average of the volumes from the independent reviews will be used for analysis.

Volume of HO at baseline and volume of new HO at post-baseline visits will be summarized with descriptive statistics. Similar summaries will be provided for those subjects in the Flare-up Population who had flare-ups with new HO at any post-baseline visit.

HO lesions will be graded according to the following scale:

- Grade 0 – Imputed when there is no new HO
- Grade 1 – Fluid attenuation without evidence of calcification at CT

- Grade 2 – Calcification of soft tissues without evidence of bone formation
- Grade 3 – Immature bone formation
- Grade 4 – Mature bone with cortical differentiation

The HO grade at baseline will be calculated as the maximum HO grade across lesions. The *new* HO grade at post-baseline visits will be calculated as follows:

1. If there is no new HO, assign new HO grade = 0.
2. If there is new HO
 - a. If there was no baseline HO, calculate the maximum HO grade across lesions.
 - b. If there was baseline HO, calculate the maximum HO grade across lesions where there was no baseline HO.

HO grade at baseline and new HO grade at post-baseline visits will be summarized with counts and percentages of flare-ups.

6.2.2 Area of HO and HO Scores

The area of HO and HO scores will be determined from x-ray for subjects unable to undergo CT scan.

Area of HO at baseline will be calculated as the sum of the areas for each lesion. The area of *new* HO at post-baseline visits will be calculated using both anterior/posterior (AP) and lateral views as follows:

1. If there is no new HO, assign new area = 0 ($NAREA = 0$).
2. If there is new HO
 - a. Subtract the area of baseline HO from the area of post-baseline HO for each lesion ($NAREA_1, NAREA_2, \dots, NAREA_L$ where L is the number of lesions).
 - b. If the area of post-baseline HO < the area of baseline HO for a given lesion i , impute new area = 0 ($NAREA_i = 0$).
 - c. Calculate the total area of new HO ($NAREA = NAREA_1 + NAREA_2 + \dots + NAREA_i$).

For each review, the maximum area from the AP or lateral view will be used for analysis.

If an adjudication review is performed, the area from the adjudication review will be used for analysis. Otherwise, the average of the areas from the independent reviews will be used for analysis.

Area of HO at baseline and area of new HO at post-baseline visits will be listed.

Area of HO and volume of HO (CT scan) will not be pooled. They will be presented in separate listings.

6.2.3 HO Lesion Scoring

HO scores will be determined from x-ray for subjects unable to undergo CT scan.

HO lesions will be scored according to the following scale:

- 0 – No HO

- 1 – Single or multiple spicules (punctate) or islands (non-contiguous) of HO
- 2 – Coalescing islands or reticular complexes of bone
- 3 – Single contiguous HO having longest dimension $\leq 1/2$ the diameter of the reference normotopic bone in any projection
- 4 – Single contiguous HO having longest dimension $> 1/2$ but ≤ 1 diameter of the reference normotopic bone in any projection
- 5 – Single contiguous HO having longest dimension > 1 but ≤ 2 diameter of the reference normotopic bone in any projection
- 6 – Single contiguous HO having longest dimension > 2 diameters of the reference normotopic bone in any projection

The HO score at baseline will be calculated as the maximum HO score across lesions. The *new* HO score at post-baseline visits will be calculated as follows:

1. If there is no new HO, impute new HO score = 0.
2. If there is new HO
 - a. If there was no baseline HO, calculate the maximum HO score across lesions.
 - b. If there was baseline HO, calculate the maximum HO score across lesions where there was no baseline HO.

HO score at baseline and new HO score at post-baseline visits will be listed.

HO lesion scores will not be pooled with HO lesion grades (CT scan) above. They will be described separately.

6.2.4 New or Enlarged HO and Severity of New HO

New HO lesions are those that did not exist at baseline. Enlarged HO lesions are lesions that existed at baseline but increased in volume by CT (or area by x-ray) post-baseline. The incidence of new HO lesions only, enlarged HO lesions only, or both new HO and enlarged HO lesions will be summarized at each scheduled visit with counts and percentages of flare-ups.

The severity of new HO (mild, moderate, severe) will be summarized at each scheduled visit with counts and percentages of flare-ups.

6.2.5 Presence of Soft Tissue Swelling (Edema) and/or Cartilage Formation, Severity of Edema, and Volume of Edema

Presence of edema and cartilage formation will be determined from MRI (or US for subjects unable to undergo MRI). Note that US does not include an assessment of cartilage formation.

If an adjudication review is performed, the severity and volume of edema from the adjudication review will be used for analysis. Otherwise, the maximum severity and the average volume of edema from the independent reviews will be used for analysis. Note also that when edema is assessed as mild with US, moderate will be imputed for analysis.

The presence of edema and the presence of cartilage formation will be summarized at each scheduled visit with counts and percentages of flare-ups.

The severity of edema (no edema, any edema, mild edema, moderate edema, severe edema, moderate or severe edema [higher intensity flare-ups]) will be summarized at each scheduled visit with counts and percentages of flare-ups.

The shift in severity of edema from baseline to each post-baseline visit will also be summarized with counts and percentages of flare-ups.

Volume of edema at each scheduled visit will be summarized with descriptive statistics.

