7.2.3 New or Enlarged HO and Severity of New HO

New HO lesions are those that did not exist at baseline. Enlarged HO lesions are lesions that existed at baseline but increased in volume (or area by x-ray) post-baseline. The incidence of new HO lesions only, enlarged HO lesions only, or both new HO and enlarged HO lesions will be summarized at each scheduled visit with counts and percentages of flare-ups.

The severity of new HO (mild, moderate, severe) will be summarized at each scheduled visit with counts and percentages of flare-ups.

7.2.4 Presence of Soft Tissue Swelling (Edema) and/or Cartilage Formation, Severity of Edema, and Volume of Edema

MRI (or US for subjects unable to undergo MRI) will be performed at:

- Screening/Baseline, Week 6, and Week 12 (Flare-up Component).

Note that US does not include an assessment of cartilage formation. If an adjudication review is performed, the severity and volume of edema from the adjudication review will be used for analysis. Otherwise, the maximum severity and the average volume of edema from the independent reviews will be used for analysis. Note also that when edema is assessed as mild with US, moderate will be imputed for analysis.

The presence of edema and the presence of cartilage formation will be summarized at each scheduled visit with counts and percentages of flare-ups.

The severity of edema (no edema, any edema, mild edema, moderate edema, severe edema, moderate or severe edema [higher intensity flare-ups]) will be summarized at each scheduled visit with counts and percentages of flare-ups.

The shift in severity of edema from baseline to each post-baseline visit will also be summarized with counts and percentages of flare-ups.

Volume of edema at each scheduled visit will be summarized with descriptive statistics.

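### Parts A and B do not say whether growth of a baseline lesion is new HO, and the volume and grade rules are incoherent on either answer

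*SAP*

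**What the plan says.** Part B SAP 6.1 sets the endpoint: "The primary efficacy endpoint is the proportion of flare-ups with no new HO at Week 12 as assessed by CT scan", or by x-ray where CT is not possible. Its only gloss is that this "means no new HO at Week 12 compared to baseline where baseline is Flare-up Day 1". Part A SAP 7.1 uses the same endpoint with the same kind of gloss. Neither section mentions enlargement.

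Part B 6.2.4 then classifies lesions: "New HO lesions are those that did not exist at baseline". Enlarged lesions are a second class; in Part A 7.2.3, "Enlarged HO lesions are lesions that existed at baseline but increased in volume (or area by x-ray) post-baseline". Both sections tabulate flare-ups at each visit as new only, enlarged only, or both.

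The derivations in Part B 6.2.1 start from new-HO status:

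- **Volume, step 1:** "If there is no new HO, assign new volume = 0".
- **Volume, steps 2a to 2c:** if there is new HO, baseline volume is subtracted from post-baseline volume for every lesion, negative differences are set to zero, and the results are summed.
- **CT grade:** 0 if there is no new HO. Otherwise, in step 2b, "If there was baseline HO, calculate the maximum HO grade across lesions where there was no baseline HO".

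For x-ray, area (6.2.2) follows the volume rule and the score (6.2.3) follows the grade rule: "If there was baseline HO, calculate the maximum HO score across lesions where there was no baseline HO". Part A 7.2.1 and 7.2.2 have the same structure.

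**The concern.** An enlarged-only flare-up is a case the plan itself expects, since it has its own row in a planned table. Yet the primary sections do not say whether it is a success or a failure, so two programmers could follow the SAP faithfully and report different primary proportions.

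The same status decides whether any volume is counted and which flare-ups receive a grade. In Part B it also defines the new-HO and no-new-HO subgroups for range of motion, CAJIS, global assessment, FOP-PFQ, PROMIS and the biomarker figures. An open classification at this point therefore carries into much of the efficacy output.

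**Working it through.** The SAP gives no figure to reproduce here, so the check applies the written rules to test flare-ups under two readings.

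**Readings.** Narrow: new HO requires a lesion absent at baseline. Broad: new HO also includes an enlarged baseline lesion.

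**Rules (Part B 6.2.1).** If there is no new HO, NVOL = 0 and grade = 0. If there is new HO, NVOL = Σ max(0, post-baseline volume − baseline volume) over all lesions. With baseline HO present, grade is the maximum over lesions that had no baseline HO.

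**Test cases (volumes in arbitrary units, chosen for illustration).**

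| Flare-up | Reading | Primary | NVOL | CT grade |
|---|---|---|---|---|
| Unchanged: A 1000 → 1000 | either | success | 0 | 0 |
| New only, no baseline HO: B 0 → 5000, grade 3 | either | failure | 5000 | 3 |
| Enlarged only: A 1000 → 6000, grade 4 | narrow | success | 0 | 0 |
| Enlarged only: same | broad | failure | 6000 − 1000 = 5000 | maximum of an empty set |
| Both: A 1000 → 6000 (grade 4), B 0 → 100 (grade 2) | either | failure | 5000 + 100 = 5100 | 2 |

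**Narrow reading.** Adding a 100-unit new lesion to identical growth moves NVOL from 0 to 5100. The 5000 units on lesion A are discarded in one case and counted in the other. That does not fit the first secondary endpoint in Part B 6.2, which is change from baseline in the amount of bone formed.

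**Broad reading.** Volume behaves sensibly, but grade step 2b has nothing to take a maximum over. Section 3 bases percentages on non-missing values, so the flare-up drops out of the CT grade table although it failed the primary endpoint. The x-ray score has the same gap in its listing.

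**Primary proportion.** Let e be the share of evaluable flare-ups that are enlarged-only. They are successes on the narrow reading and failures on the broad one, and nothing else changes, so p(narrow) − p(broad) = e.

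The documents do not give e. As an illustration only, assume 40 flare-ups and p(narrow) = 70%. The asymptotic 95% interval planned in Part B 6.1 is p ± 1.96 × √(p(1 − p)/40):

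| Assumed e | Proportion | 95% CI |
|---|---|---|
| narrow reading | 70% | 55.8 to 84.2 |
| broad, 5% | 65% | 50.2 to 79.8 |
| broad, 10% | 60% | 44.8 to 75.2 |
| broad, 20% | 50% | 34.5 to 65.5 |

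**The case against.** The strongest reply is that the text already leans to the broad reading. The lesion classification defines new HO *lesions*; it does not define the flare-up-level term, and the primary section does not import it. Volume steps 2a and 2b have work to do only for lesions that existed at baseline. The Part A description of the Global Read speaks of the presence of HO, including whether a lesion is new and/or enlarged. This stands. A reader might infer that the written definition makes bone growth a success and so inflates the primary proportion, but the documents do not establish that. The lean is nowhere turned into a statement, however, and the broad reading is the one that leaves the grade undefined.

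Second, the narrow reading gives a consistent triple for an enlarged-only flare-up (success, volume 0, grade 0), and limiting a new-HO grade to new lesions is a defensible choice of estimand. That is fair for grade. It does not rescue volume, where the same growth counts as 0 or 5000 units depending on an unrelated small lesion.

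Third, the three-way table discloses the enlarged-only count, so a reader could convert one proportion into the other. This is true and lowers the severity. It does not repair volume, grade or the subgroups.

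Fourth, a reader might infer that a table of x-ray scores is also distorted. None is planned: scores and areas are only listed.

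Finally, the protocol, which is not shown, may say how readers call new HO. The Part B SAP cites the review charter only for reader agreement, and the SAP's derivation rules would still need to match.

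**Conclusion.** The point holds and should be fixed. Parts A and B leave the primary classification of enlarged-only flare-ups open, and a derivation rule fails whichever way it is closed: new volume on the narrow reading, CT grade (and the listed x-ray score) on the broad one.

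The effect on the primary proportion is exactly the enlarged-only share. Its size cannot be computed from the documents; the 5% to 20% range, the 40 flare-ups and the 70% are assumptions. The direction of any error is also not established, because it depends on which reading was programmed. The logical results rest only on the rules as written.

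**What to change.** 1. In Part A 7.1 and Part B 6.1, state that new HO for the primary endpoint means a new lesion or an enlarged baseline lesion as called by the readers, in line with volume step 2a. The new-HO condition in the volume and area rules then carries the same meaning.
2. State that enlargement follows the reader or adjudicated call. The lesion definitions count any increase in volume or area as enlargement, and without this statement measurement noise alone could turn a stable lesion into a primary failure.
3. Change step 2b of the grade and score rules (Part A 7.2.1 and 7.2.2; Part B 6.2.1 and 6.2.3) to the maximum across lesions that are new or enlarged, so that enlarged-only flare-ups receive a value.
4. Report the strict new-lesion-only proportion beside the primary one, using the existing three-way split.

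The cost is SAP wording and re-derivation from lesion-level reads that the plan already requires. The primary proportion may be less favourable than on the narrow reading. The grade given to an enlarged lesion may simply be the grade it had at baseline, which a table footnote can say.

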6.2.6 Active Range of Motion

Range of motion at the primary and secondary joints will be assessed using a goniometer. The primary joint will be indicated on the eCRF and all other joints will be considered secondary.

Arcs of motion as defined in Table 1 will be calculated based on raw ROM measurements. If any of the contributing raw ROM measurements are missing, the arc of motion will not be calculated. Percent of normal arc of motion will be calculated as $100 \times \text{arc of motion} / \text{normal adult arc of motion}$.

Table 1. Arcs of Motion

Joint	Arc of Motion	Calculation Based on Raw ROM Measurements	Normal Adult Arc of Motion (degrees)
Hip	Extension/Flexion	Extension + Flexion	140
	Abduction/Adduction	Abduction + Adduction	60
	Total Arc of Motion	Extension + Flexion + Abduction + Adduction	200
Knee	Total Arc of Motion	Extension + Flexion	135
Shoulder	Total Arc of Motion	Flexion + Abduction-glenohumeral + Abduction-shoulder complex	490
Elbow	Extension/Flexion	Extension + Flexion	150
	Supination/Pronation	Supination + Pronation	160
	Total Arc of Motion	Extension + Flexion + Supination + Pronation	310
Wrist	Total Arc of Motion	Extension + Flexion	150
Ankle	Dorsiflexion/Plantarflexion	Dorsiflexion + Plantarflexion	70
	Subtalar Inversion/Subtalar Eversion	Subtalar Inversion + Subtalar Eversion	50
	Total Arc of Motion	Dorsiflexion + Plantarflexion + Subtalar Inversion + Subtalar Eversion	120
Cervical Spine	Extension/Flexion	Extension + Flexion	90
		Lateral	45
		Rotation	60
	Total Arc of Motion	Extension + Flexion + Lateral + Rotation	195
Jaw	Total Arc of Motion	Opening	35 mm
Lumbar Spine	Total Arc of Motion	Flexion	6 cm
		Extension	1 cm
		Flexion + Extension	7 cm

Source: Norken and White (2011)¹

Percent of normal arc of motion values and changes from baseline will be summarized at each scheduled visit with descriptive statistics. Summaries will be provided separately for:

- Percent of normal total arc of motion at the primary joint (subjects have one total arc of motion at the primary joint)
- Percent of normal arc of motion at the primary joint by joint and arc of motion (subjects may have more than one arc of motion at the primary joint)
- Percent of normal arc of motion at the secondary joints by joint and arc of motion (subjects may have more than one arc of motion at one or more secondary joints)

Similar summaries for percent of normal total arc of motion will be provided for subgroups defined by presence of new HO at any post-baseline visit (new HO, no new HO).

